### ***Study Conditions***

Participants will be electronically randomized into one of five groups to examine relative effectiveness of and parent preferences for different methods of framing child passenger safety (CPS) recommendations. The five study conditions (four versions of CPS recommendations and one control group) are described below and are included in the attachments.

#### *CPS Message Alternate 1: CPS Recommendations that Focus on Natural Progression.*

Participants assigned to this condition will view an alternate version of the NHTSA CPS recommendations in which both text and pictures will highlight the natural progression of seat types from birth to teen years. This version of recommendations removes almost all references to age and all mention of upper limits for common seats as a factor for determining transitions. Recommendations for transitioning from rear-facing to forward-facing will push toward later transition. To quell the perception that age 8 is the maximum, it is mentioned that it can take up to 12 years or longer for a child to be big enough to use a safety belt alone. Recommendations for this condition will focus on best practice for determining transitions to the next stage, which include child size and fit of the restraint. For instance, transition to safety belts will focus on fit of the belt on the seated child (using the fit test), with usual *maximum* height for a booster seat (4'9") given as additional guides. Pictures will be used to emphasize the upper transition norms for each stage. The need for back seat positioning will also be more fully integrated and highlighted throughout the recommendations. (See Appendix E; Illustration 1)

*CPS Message Alternate 2: CPS Recommendations that Draw Attention to Premature Graduation.* Participants assigned to this condition will view an alternate version of the NHTSA CPS recommendations in which both text and pictures draw attention to premature graduation. Therefore, in addition to specifying recommendations for each stage, this version of recommendations specifically emphasizes the message that counters premature graduation to the next stage. For instance, "Stage 2: Forward-facing seats" is changed to "Keep Kids in Harnesses as long as Possible" to emphasize the need to use harnesses throughout this stage. Parents are encouraged to keep children in harnessed seats for as long as the harness weight and height limit will allow. Accompanying pictures provide additional emphasis. Similar to alternate one, this

version of recommendations also removes almost all references to age and upper limits for common seats, and fully integrates and highlights the need for back seat positioning at all stages. (Appendix E; Illustration 2)

*CPS Message Alternate 3: CPS Recommendations that Explain Risk Reduction/Rationale.*

In order to be consistent with the risk communication literature and maximize behavior change, this version of the CPS recommendations communicates the risk reduction and rationale (in a lay-friendly, succinct manner avoiding statistics) behind each stage's recommended restraint configuration, starting first with the basic rationale for occupant restraints, and moving into rationale for specific restraint configurations for the various child sizes. For example, many parents lack the understanding that an object in motion remains in motion when the vehicle crashes, unless restrained. They also fail to grasp that given the abrupt changes in momentum and velocity that occur in mere fractions of a second, crash forces are quite powerful and can result in a child propelling forward with the force of thousands of pounds. Similar to alternate one, this version of recommendations also includes pictures to illustrate stages of restraints, removes almost all references to age and upper limits for common seats, and fully integrates and highlights the need for back seat positioning at all stages. (Appendix E; Illustration 3)

*Comparison: Current CPS Recommendations.* Participants assigned to this condition will view NHTSA's current CPS recommendations as depicted in the "Car Seat Recommendations for Children" flyer released March 2011 (NHTSA, 2011). (Appendix E; Illustration 4)

*Control Group.* Participants assigned to this condition will not receive any instructional materials related to CPS during their participation. Rather, these participants will be taken through a computerized pictorial display of various child safety seats and motor vehicles currently on the market and asked to rate their preferences based on style, color, and other characteristics (See Appendix F). This subterfuge will allow for elapsed time between their pretest and posttest measures as in the other study conditions. To avoid a missed opportunity to educate, control group participants (and all participants) will be given a handout on child passenger safety to take home for reference once they have *completed* participation in the study (see post-study information handout in Appendix M).

## **Measures**

Several measurement scales will be used to assess appropriateness of restraint selection, knowledge of restraints, perceived efficacy and threat, attitudes and intentions, judgments of relevance and acceptability of the CPS information, and sample demographics. To accurately assess changes in knowledge and perceptions after exposure to the independent variable, most measures will be asked both at pretest and posttest. The exceptions are the demographics questions and judgments of relevance and acceptability, which will be asked only at posttest (see survey attachment in Appendix H).

*Restraint Selection Task.* A key dependent variable for Study 1 is proper child restraint selection; thus, a Restraint Selection Task was developed that provides participants with a series of specific scenarios that ask the participants to select an appropriate restraint, direction to face, and/or vehicle row, given specific age/weight/height information for a hypothetical child. This 8-item knowledge measure uses a multiple choice response format (providing an item score of correct/incorrect and a total number correct score for each participant). This measure was adapted

from a similar existing field-tested measure (Snowden et al., 2008).

*Knowledge of Restraint.* To gauge immediate changes in knowledge of child passenger safety, as well as differences in knowledge among the groups, a 15-item assessment of parental knowledge will be conducted at both pretest and posttest. This measure uses a Likert-type response format and was tailored for this study from existing field-tested and validated measures used in past research by Snowden and colleagues (2008, 2009), and Will and colleagues (2009). Many questions originated from the Co-Investigators Kids in Kars Survey which has excellent internal consistency ( $\alpha = .92$ ) and measures parents' knowledge of and attitudes toward recommended guidelines for restraint use (Will, Sabo, & Porter, 2009).

*Perceptions of Efficacy and Risk.* The Risk Behavior Diagnosis Scale (RBDS) (Witte, Cameron, McKeon, & Berkowitz, 1996) will be used to assess perceived efficacy and risk. The RBDS is a 12-item template survey designed to be tailored for assessment of any health or safety message. The efficacy subscale (internal consistency  $\alpha = .79$ , 6 items) assesses participants' perceptions of response efficacy (i.e., confidence that the recommended actions/restraints will work to prevent injuries) and self-efficacy (i.e., confidence in one's ability to follow child passenger safety recommendations). The threat subscale (internal consistency  $\alpha = .82$ , 6 items) assesses participants' perceived risk by measuring susceptibility to and severity of negative consequences from inappropriate child occupant protection. Four additional "severity" items were added to properly assess perceptions of severity of the threat at each of the four stages of occupant protection. This, the final RBDS contains 16 items, all of which use a 5-point Likert-type response scale (1 = strongly disagree to 5 = strongly agree).

*Attitudes and Intentions.* Participant's more general attitudes and intentions regarding child passenger safety will be assessed via an 8-item attitudes subscale, adapted from the previously mentioned Kids in Kars survey (Will, Sabo, & Porter, 2009), and a 9-item stated intentions subscale. Stated intentions and attitudes will be assessed to gauge participants' disposition regarding what is recommended for child occupant protection irrespective of their knowledge. Both subscales use a Likert-type response format (1 = strongly disagree to 5 = strongly agree).

*Judgments of Relevance and Acceptability.* At posttest, parents in each condition will be asked their opinions about the CPS materials. A 10-item questionnaire was developed that uses a 4-point Likert-type response format to assess participants' judgments of quality and acceptability of the CPS information presented. Specifically, they will be asked to rate the CPS information on a variety of factors, including but not limited to style, amount of information, clarity, and likelihood for motivating behavior change.

*Demographics and Other Participant Information.* Demographic information will also be collected at the posttest, including but not limited to participant's age, sex, race, ethnicity, education level, income level, and number of and ages/sizes of children. Information specific to child passenger safety will also be assessed, including types of child restraints being used currently (by child), sources of information about safely transporting children, whether or not they have had their child restraints inspected by a CPS technician, and their preferred communication channels (e.g., print, television, radio, electronic) for receiving child passenger safety information.

### ***Data Analysis Plan***

Data analysis will determine which CPS recommendation version produces the maximum desired outcome (e.g., correct CPS restraint selection, increased knowledge of restraints, enhanced perceptions of efficacy and risk). Data analysis will begin with data cleaning such as checking for missing data and outliers and ensuring normality and linearity of all dependent variables. Next, bivariate correlations will be conducted on all dependent variables to assess their relation to each other and to determine the type of inferential statistics to conduct. Specifically, if dependent variables are moderately inter-correlated, then a 2 (Time) x 5 (CPS Recommendation Version) MANOVA with follow-ups, post-hoc test for group, and simple effects analyses (if the interaction is significant) will be conducted. If dependent variables exhibit inter-correlations near zero or are highly inter-correlated, then multiple 2 (Time) x 5 (CPS Recommendation Version) ANOVAs with post-hoc test for group and simple effects analyses (if the interaction is significant) will be conducted. In the event that the data are found to violate the assumptions of normality that are necessary for parametric tests, data transformations to improve normality or appropriate nonparametric tests, such as the Friedman test and follow-up Multiple Comparison Tests, will be performed instead. Additionally, the study team may conduct several secondary analyses, including a multiple regression for CPS restraint selection to determine which CPS recommendation version best predicts correct restraint selection. Also, variables such as perceived relevance and accuracy of CPS information, age, sex, race, education, income, number of children, and ages of children may be used as covariates to eliminate potential confounding variables and better explain variance in the analyses. The results of Study 1 will be written into a brief research report for NHTSA. No reports or presentations will identify individual participants.

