## Research Overview

The purpose of this research is to assess various methods of framing NHTSA's CPS recommendations, as well as the scope of the information provided. This project will conduct two experimental studies. Data will be collected from parent participants in two large metropolitan statistical areas on the east coast of the United States. In the first study, participants (N= 300) will be randomized into one of five groups to examine relative effectiveness of, and parent preferences for, different methods of framing CPS recommendations. That is, the goal of the first study is to determine HOW to best communicate the recommendations to parents (e.g., should we include information regarding risk- reduction/rationale, should we emphasize the "hardest sell" for advocates over all other information, etc.). In the second study, participants (N= 240) will be randomized into one of four groups to examine the relative effectiveness of CPS recommendations delivered in combination with other types of information. That is, the goal of the second study is to determine the type and amount of EXTRA information to include in the recommendations without losing the clarity and power of the key recommendations (e.g., normative information is often included but theoretically is contra-indicated, installation information is not included but theoretically may be necessary, etc.). It is hoped that the findings of this research inform the development of more effective ways to communicate messages for child passenger safety. These studies and their methods are explained in detail in the sections that follow.

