## Study 1 Methods

### *Study Design*

For Study 1, a 5 (CPS Recommendation Version) X 2 (Time) experiment will use a randomized controlled trial design to examine relative effectiveness of and parent preferences for different methods of framing child passenger safety recommendations. As described in more detail below, parent participants will be electronically randomized to one of five groups (including four experimental conditions and one control group), and will respond to pre-post surveys.

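### Study 1's five-level Time x Version test includes the no-message control, so a significant result cannot separate an effect of framing from an effect of seeing any message

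*Protocol*

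**What the plan says.** The Research Overview gives the purpose of Study 1: "the goal of the first study is to determine HOW to best communicate the recommendations to parents". It describes the randomization as "to examine relative effectiveness of, and parent preferences for, different methods of framing CPS recommendations". The Study 1 Data Analysis Plan restates the aim: "Data analysis will determine which CPS recommendation version produces the maximum desired outcome".

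The Study Design section describes the five groups as "including four experimental conditions and one control group". Under Study Conditions, four groups see a version of the recommendations: three alternates and a comparison arm, for which "Participants assigned to this condition will view NHTSA's current CPS recommendations". The fifth group is different in kind: "Participants assigned to this condition will not receive any instructional materials related to CPS during their participation". It rates pictures of seats and vehicles instead.

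The Data Analysis Plan enters all five groups as levels of one factor, CPS Recommendation Version, in a 2 x 5 MANOVA or in several 2 x 5 ANOVAs. A post-hoc test for group follows, without a named procedure. Simple effects are conditional on a significant interaction. No contrast among the message versions is specified. The only other route is an optional regression, for which no reference arm is given.

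**The concern.** The stated aim concerns differences among versions of the recommendations, and the control group sees no version. If reading any of the four messages raises scores and the control does not change, the Time x Version test can be significant even though the four messages work equally well. A reader of the report to NHTSA could take that result as evidence that framing matters.

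The comparisons that do answer the aim are left to a post-hoc step. If that step covers all five arms, part of its error rate is spent on pairs that involve the control, and the message-versus-message comparisons lose power.

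**Working it through.** **Inputs.** N = 300 in five groups (Research Overview). The allocation ratio is not stated, so 60 per arm is assumed. Alpha 0.05, power 0.80, effect 0.25 and a required sample of 196 come from the Study 1 Sampling Plan, which also cites effects of d = 0.50 to 1.68 from similar message studies. One outcome is considered, with SD 1.

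**1. The plan's own figure.** For a one-way omnibus F test with k groups, the noncentrality is λ = N f², with k − 1 and N − k degrees of freedom. With k = 5 and f = 0.25, N = 196 gives λ = 196 × 0.0625 = 12.25 and power 0.8005, while N = 195 gives 0.798. So 196 is reproduced as the size for a five-group omnibus test. (A 2 x 5 interaction with f = 0.125 and pre-post correlation 0.5 has the same λ.) It is not the size for a two-arm contrast: two arms at d = 0.25 with 80% power need 252 per arm.

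**2. Only the control differs.** Let the four message means be equal and the control lower by D. The between-group variance is D² × 0.2 × 0.8, so f = 0.4 D and λ = 300 × 0.16 × D² = 48 D². The critical F(4, 295) is 2.402.

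| D (SD) | λ | P(significant) |
|---|---|---|
| 0.25 | 3.00 | 0.24 |
| 0.50 | 12.00 | 0.795 |
| 0.80 | 30.72 | 0.997 |

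For the Time x Version interaction, λ is divided by 2(1 − ρ), where ρ is the pre-post correlation. The table applies unchanged at ρ = 0.5. At D = 0.50:

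- ρ = 0.3: λ = 12/1.4 = 8.57, probability 0.63
- ρ = 0.7: λ = 12/0.6 = 20, probability 0.96

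The protocol gives no ρ, so this is an assumed range.

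**3. Power for one message against another.** The noncentrality is d × √(60/2) = d × 5.477, which is 2.739 at d = 0.5 and 3.286 at d = 0.6. Error df is 295.

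| Procedure (assumed) | Critical t | d = 0.5 | d = 0.6 |
|---|---|---|---|
| Tukey, five arms (10 pairs) | 2.745 | 50% | 71% |
| Tukey, four message arms (6 pairs) | 2.584 | 56% | 76% |
| Dunnett, three alternates v current flyer | 2.361 | 65% | 82% |

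Removing the control from the family gives the step from row 1 to row 2, about 5 to 6 points. The step from row 2 to row 3 comes from giving up the alternate-versus-alternate pairs.

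**4. Does the follow-up protect against misreading?** In 40,000 simulated trials with only the control different (D = 0.5), follow-up tests after a significant five-arm F gave these false findings:

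| Follow-up | Some alternate v flyer | Any of the six message pairs |
|---|---|---|
| Tukey, five arms | 1.7% | 3.2% |
| Unadjusted pairwise | 11.8% | 18.9% |

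**The case against.** The strongest reply is that the plan does not stop at the five-level test. It lists follow-ups, and step 4 shows that error-controlled follow-ups would largely prevent a control-driven result from being read as a framing effect. That stands. The risk of misreading depends on reporting the omnibus result alone or on choosing unadjusted tests, and the protocol commits to neither.

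Three stronger readings are tempting, and the document does not support them.

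- **That only the three alternate-versus-flyer contrasts matter.** The flyer arm is labelled as the comparison, but the aim is to find the best version, so all six pairs among the four messages are relevant. The whole gap between 50% and 65% at 0.5 SD therefore cannot be blamed on including the control.
- **That the plan prescribes all-pairs tests behind an omnibus gate.** No post-hoc procedure is named, and the condition on a significant interaction is attached to the simple effects, not clearly to the post-hoc test.
- **That the five-level test says nothing about framing.** It responds to differences among messages as well. The trouble is that it is not specific to them.

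It may also be said that naming the post-hoc test belongs in a statistical analysis plan. That is fair, and the missing name is not the point here. The protocol itself already fixes the five-level factor with the control inside it.

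**Conclusion.** The concern holds in a limited form. The planned Study 1 test cannot separate a framing effect from an any-message effect. With four identical messages and a control 0.5 SD lower, which is the bottom of the effect range that the protocol cites, it is significant about 80% of the time (63% to 96% over the assumed correlations). At 0.25 SD and correlation 0.5 the figure is 24%.

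The power cost of keeping the control in the family is modest: about 5 to 6 points for a message-versus-message difference of 0.5 to 0.6 SD. That figure is conditional on Tukey over all five arms, which is an assumption.

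All figures assume 60 per arm and a single outcome. Excluding participants who click through too fast, or adjusting for several outcomes, would lower the power figures. A reader might infer that the plan will produce false claims about framing; that does not follow if the follow-up tests control error.

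**What to change.** In the Study 1 Data Analysis Plan:

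1. Make the comparisons among the four message versions (three alternates and the current flyer) the primary family. Use error-controlled tests, for example Tukey over four arms, on posttest scores adjusted for the pretest, with no five-arm omnibus gate.
2. Report the messages versus the control separately, as a check that the measures respond to any message.
3. If the sponsor's main question is only whether an alternate beats the current flyer, say so and use Dunnett for those three contrasts. Power rises to 65% at 0.5 SD and 82% at 0.6 SD, at the cost of making alternate-versus-alternate comparisons secondary.

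The cost is analysis wording. The pretest is already collected for most measures, and no arm, participant or procedure changes. Pretest adjustment adds to the power in the working: at a correlation of 0.5, a 0.5 SD difference becomes 0.5/√0.75 = 0.58 residual SD, and four-arm Tukey power goes from 56% to 72%.

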### *Sampling Plan*

The geographic regions in which the study will take place include two large Metropolitan

Statistical Areas (MSAs): Philadelphia – Camden – Wilmington (Delaware Valley) and Virginia Beach – Norfolk – Newport News (Hampton Roads). The Delaware Valley MSA includes 13 counties in four States with a population of over 5.9 million people. The Hampton Roads MSA includes 10 cities and six counties in two States (VA-NC), with a population of over 1.6 million. These are two socio-economical and culturally diverse areas that range from the rural areas of VA's Eastern Shore and PA's farming communities, to large concentrations of people living in urban and suburban settings.

The sample will include 300 parents of children ages 0-12 years. Although expected to be a convenience sample, efforts will be made during recruitment and screening of participants to ensure that the sample under study is representative of the larger population, and that the study includes a variety of income levels, education levels, and racial/ethnic groups (at least Black, White, Latino) across the study conditions.

Power analysis indicated that a sample of 196 participants is adequate to detect small effect sizes above Cohen's  $d = 0.25$  with a statistical power of 0.80 at the standard significance level of  $\alpha = .05$ . Equal variance between groups is expected due to random assignment. Effect sizes for similar studies of intervention messages with smaller sample sizes and fewer experimental groups have been in the medium to large range (Cohen's  $d = .50$  to 1.68) (Will, Sabo, & Porter, 2009). Therefore, the sample size of 300 participants will be ample to detect group differences in this study.

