### ***Procedure for Participation***

Study 2 will follow the same general procedure for participation as in Study 1. Enrolled participants will arrive at a designated computer lab/center, at which point the study assistant will help them log into a secure web-based study protocol to view a series of user-friendly screens that will automatically lead them through the informed consent document, pretest measures, study materials specific to condition assignment (described separately below), and post-test measures at the participant's pace. (See Flow Diagram of Study 2.) Procedures similar to those used in Study 1 will be used regarding orienting participants to the study materials, obtaining informed consent, de-identifying data, performing manipulation checks of data, and for data management and security of data.

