## **Data Analysis Plan**

Analyses will determine which CPS information combination produces the maximum desired outcome (e.g., correct CPS restraint selection, increased knowledge of restraints, increased perceptions of efficacy and risk, increased knowledge of common mistakes). This will initially consist of data cleaning such as checking for missing data and outliers and ensuring normality and linearity of all dependent variables. Next, bivariate correlations will be conducted on all dependent variables to assess their relation to each other and to determine the type of inferential statistics to conduct. Specifically, if dependent variables are moderately correlated, then a 2 (Time) x 4 (CPS Information Combination) MANOVA with follow-ups, post-hoc test for group, and simple effects analyses if the interaction is significant will be conducted. If dependent variables exhibit correlations near zero or are highly correlated, then multiple 2 (Time) x 4 (CPS Information Combination) ANOVAs with post-hoc test for group and simple effects analyses if the interaction is significant will be conducted. In the event that the data are found to violate the assumptions of normality that are necessary for parametric tests, data transformations to improve normality or appropriate nonparametric tests, such as the Friedman test and follow-up Multiple Comparison Tests, will be performed instead. Additionally, the study team may conduct several secondary analyses, including a multiple regression for CPS restraint selection to determine which CPS information combination best predicts correct restraint selection. Also, variables such as perceived relevance and accuracy of CPS information, age, sex, race, education, income, number of children, and ages of children may be used as covariates to eliminate potential confounding variables and better explain variance in the analyses.

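### The post-hoc test for group in the Time x Group analysis averages in the pretest and so sees only half of any message effect; posttest means adjusted for the pretest would compare the arms better at no cost

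*Protocol*

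**What the plan says.** The Study 1 Data Analysis Plan aims to find which version of the recommendations gives the best outcome. If the dependent variables are moderately correlated, "then a 2 (Time) x 5 (CPS Recommendation Version) MANOVA with follow-ups, post-hoc test for group, and simple effects analyses" follow, and the sentence goes on to make the simple effects depend on a significant interaction. Otherwise it plans separate "ANOVAs with post-hoc test for group and simple effects analyses (if the interaction is significant) will be conducted". The Study 2 Data Analysis Plan has the same structure: "then a 2 (Time) x 4 (CPS Information Combination) MANOVA with follow-ups, post-hoc test for group, and simple effects analyses".

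Under Measures, "most measures will be asked both at pretest and posttest"; demographics and the judgments of relevance and acceptability are posttest only. The order within the session is "pretest measures, study materials specific to condition assignment (described separately below), and post-test measures at the participant's pace" (Study 2, Procedure for Participation; Study 1 describes the same order). The pretest therefore enters the planned model as one level of Time. The optional covariates are perceived relevance and accuracy plus demographics: "age, sex, race, education, income, number of children, and ages of children may be used as covariates".

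**The concern.** Under randomisation a message can move only the posttest. In a Time x Group model the group term averages over Time, so a post-hoc test on it compares arms on a quantity of which half was recorded before exposure. It is also the one arm-versus-arm comparison that the text does not clearly make conditional on the interaction.

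The interaction shows that change differs somewhere among the groups, but not which version is better. The planned route to that answer, group compared at posttest, opens only after a significant interaction and, in its usual form, ignores the pretest score. At stake is whether the comparison that picks a version makes good use of data already being collected.

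**Working it through.** **Inputs.** From the protocol: N = 300 in five groups (Study 1), N = 240 in four groups (Study 2), effect size 0.25, power 0.80, alpha .05. Assumed: equal allocation (60 per arm), equal pretest and posttest SD, two-sided pairwise tests, and r = 0.3, 0.5, 0.7.

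**Step 1: the protocol's own figure.** The Study 1 Sampling Plan states: "Power analysis indicated that a sample of 196 participants is adequate to detect small effect sizes above Cohen's" d = 0.25. A one-way ANOVA on a single measurement with f = 0.25 and noncentrality N f² gives power 0.798 at N = 195 and 0.801 at N = 196, so 196 is reproduced. With four groups it gives 0.799 at 178 and 0.802 at 179, which reproduces the Study 2 figure. As Cohen's d, 0.25 would need 252 per arm for two means, so the figure is read as f below. Both numbers describe a single-occasion comparison, not the group term of a Time x Group model.

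**Step 2: what each test carries.** Let D be the true posttest difference in SD units, with no pretest difference.

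- Group main effect: difference D/2, SD √((1+r)/2); standardised D / √(2(1+r))
- Interaction (change score): difference D, SD √(2(1−r)); standardised D / √(2(1−r))
- Posttest simple effect: difference D, SD 1
- ANCOVA: difference D, residual SD √(1−r²); standardised D / √(1−r²)

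The ANCOVA variance is (1−r²) / (2(1−r)) = (1+r)/2 of the change-score variance: 25% lower at r = 0.5. The group main effect has (1−r²) / (2(1+r)) = (1−r)/2 of ANCOVA's information: 25% at r = 0.5.

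**Step 3: pairwise power, D = 0.5, 60 per arm, unadjusted (noncentral t).** At r = 0.5 the standardised effects are 0.5/√3 = 0.289, 0.5/√1 = 0.500, 0.500 and 0.5/√0.75 = 0.577.

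| r | Group main effect | Interaction (change) | Posttest simple effect, before gating | ANCOVA |
|---|---|---|---|---|
| 0.3 | 39% | 63% | 78% | 81% |
| 0.5 | 35% | 78% | 78% | 88% |
| 0.7 | 31% | 94% | 78% | 97% |

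With Bonferroni for the 10 pairs in Study 1 (alpha 0.05/10 = 0.005) and r = 0.5, the group test has about 11% and ANCOVA about 62%.

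**Step 4: omnibus power at f = 0.25.** N f² is 300 × 0.0625 = 18.75 in Study 1 and 240 × 0.0625 = 15 in Study 2. It is divided by 2(1+r) for the group main effect, by 2(1−r) for the interaction and by 1−r² for ANCOVA (one error degree of freedom fewer). In Study 1 at r = 0.5 this gives 6.25, 18.75 and 25.

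| Study | r | Group main effect | Interaction | ANCOVA |
|---|---|---|---|---|
| 1 | 0.3 | 55% | 84% | 97% |
| 1 | 0.5 | 48% | 95% | 99% |
| 1 | 0.7 | 43% | 99.8% | 99.9% |
| 2 | 0.3 | 49% | 78% | 94% |
| 2 | 0.5 | 43% | 91% | 97% |
| 2 | 0.7 | 39% | 99% | 99.8% |

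For 80% power in Study 1 at r = 0.5, the group main effect needs 578 participants, the interaction 196 and ANCOVA 149.

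**The case against.** The strongest reply is that the plan does not rest on the group main effect. It tests the interaction and then simple effects, and both carry the whole message effect. In an ordinary factorial reading, a significant interaction makes the simple effects the interpreted result; the bracketed condition may even govern the post-hoc test as well. Change-score analysis and ANCOVA are both valid under randomisation, so the choice between them is one of efficiency. The covariate list is open-ended, and the pretest is already in the model through Time.

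Most of this stands. A reader might infer that the Time x Group analysis as a whole halves the effect, or that the plan would routinely miss versions that truly differ. The protocol does not support either: at f = 0.25 and N = 300 the planned interaction test has 84% to 99.8% power over the r values shown. Nor does the absence of the pretest from the covariate list show that pretest data are ignored.

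What the reply does not remove is that a post-hoc test for group is named without saying that it must not choose between versions. The posttest simple effect also stays at 78% pairwise power whatever r is, before any loss from gating. Against the better of the two full-effect contrasts at each r, ANCOVA still gains about 4, 10 and 3 points at r = 0.3, 0.5 and 0.7 (Step 3, from unrounded values).

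**Conclusion.** The point holds for the post-hoc test for group, in both studies. That the group term carries half of the message effect is algebra and needs no assumption beyond randomisation and a pretest taken before exposure. Its power, 39/35/31% pairwise in Step 3 and 55/48/43% omnibus in Study 1, falls well short of the 80% on which the sample size was justified.

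Against the interaction the case is one of efficiency. The Study 1 omnibus gain is about 12 points at r = 0.3, 4 at 0.5 and almost none at 0.7. It would be tempting to call ANCOVA clearly more powerful than everything planned, but the protocol gives no pre-post correlation, and at high r the interaction is nearly as good. The figures also rest on equal variances, equal allocation for the pairwise results, and reading 0.25 as f. Outcomes measured only at posttest are unaffected.

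**What to change.** In both Data Analysis Plans, for every outcome measured at pretest and posttest, compare arms on posttest means adjusted for that outcome's pretest score (ANCOVA). If a multivariate test is kept, use MANCOVA with the pretest scores as covariates. State that the post-hoc test on the group main effect of the Time x Group model will not be used to decide between versions or information combinations. Leave posttest-only outcomes as planned.

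The cost is a change of wording. The pretest is already collected, and no added participants, measures or visits are needed.
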